- That I will be responsible for maintaining each patient's consent form in the study file and provide each patient with a signed copy of the consent form.

Investigator Name and Title:

Institution Address:

Signature: _____

Date: _____

PROTOCOL SUMMARY

Title: *"Nitroglycerin vs. Furosemide using Lung Ultrasound Pilot Trial" (N-FURIOUS)*

[figure not shown]
Précis: Of the one million admissions for AHF in the US, approximately 80% are initially managed in the ED. Outcomes from AHF are poor: nearly 25% are dead or re-hospitalized within 30 days of discharge. The evidence base to treat AHF is limited. In fact, there are no pharmacologic therapies with Class I, Level A guideline recommendations. The acute

treatment of patients today is largely the same as 40 years ago. This proposal aims to build the evidence base for ED AHF care.

Using a two-site, randomized controlled design, this pilot study will test whether a nitrate intense strategy more effectively reduces congestion, defined by LUS B-lines, better than a diuretic intense strategy.

Objectives:	1: To determine whether a nitrate intense strategy safely reduces congestion, defined by LUS B-lines, better than a diuretic intense strategy. 2: To demonstrate feasibility of recruitment and compliance with study protocol to inform future study design and enrollment projections, an external site will also test our study protocol.
Endpoint	A comparison of total B-lines at the conclusion of ED AHF management or maximum of 6 hours after enrollment, whichever comes first.
Population:	Emergency department (ED) AHF patients. All patients who meet inclusion and no exclusion criteria will be enrolled during their ED visit within 3 hours of presentation.
Phase:	2
Number of Sites enrolling participants:	Two sites (3 total hospitals). Projected sample size, n=70.
Description of Study Agent:	Nitrate intense vs. Diuretic intense AHF treatment strategy
Study Duration:	2 years. There will be three months of start up, and one month of study conclusion work. Enrollment will occur over 20 months, which equals 3.5 patients month. As there will be staggered start up to determine replication, approximately 1-2 patients/month.
Participant Duration:	30 days post discharge

SCHEMATIC OF STUDY DESIGN

*whichever comes first

**Presentation is defined as first time recorded when placed in a room to be treated. This allows patients to still be enrolled despite a long waiting room time

2 INTRODUCTION: BACKGROUND INFORMATION AND SCIENTIFIC RATIONALE

2.1 BACKGROUND INFORMATION

Over one million hospitalizations for AHF occur every year in the US. Within 30 days after hospitalization, over 25% of AHF patients will be dead or re-hospitalized.²⁵ By one year after hospitalization, up to 67% of patients will be re-hospitalized and 36% will be dead.²⁶ Worldwide, the costs of AHF exceed 100 billion annually.²⁷ For patients aged 65 years and older, AHF is the most common and most expensive reason for hospitalization.²⁸ Despite major reductions in morbidity and mortality for chronic HF, considerably less progress has been seen in AHF.²⁹⁻³¹

The emergency department (ED) initiates diagnosis and management for the vast majority of AHF patients. Nearly 80% of all admissions originate from the ED. Delays in diagnosis, misdiagnosis, and delayed or improper treatment are costly, associated with greater morbidity and mortality.^{32,33} Despite this crucial starting role, **ED AHF pharmacological management today is largely the same as 40 years ago.**³⁴ In fact, guidelines state: *“the treatment of AHF remains largely opinion-based with little good evidence to guide therapy.”*³⁵ Consensus statements from the American Heart Association as well as a working group from the NHLBI on ED AHF management further corroborate this lack of evidence: *“the evidence base on which this foundation of acute care is built is astonishingly thin.”*^{9,12} There remains a critical unmet need for evidence based ED AHF management.

2.2 RATIONALE

Limitations of Current AHF Therapy

There are currently no Class I, Level of Evidence A therapeutic guideline recommendations for AHF, highlighting the unmet need.^{4,5} In fact, therapeutic recommendations from the ACCF/AHA begin with hospital based management, highlighting the absence of ED based evidence.³⁷ The last ED based guidelines were published in 2007 and have yet to be updated.⁴² We argue this lack of evidence leads to tremendous variation in ED care. Combined, this contributes to worse outcomes.

Targeting Congestion in AHF

Freedom from congestion is associated with improved outcomes;⁴³⁻⁴⁸ yet many patients leave the hospital inadequately decongested.^{43,49-52} In fact, many patients leave the hospital without a pre-discharge assessment of congestion.^{38,39} We would argue many ED AHF patients are poorly assessed *prior* to hospitalization. The absence of robust, reliable methods to assess congestion is a primary reason why it is not assessed.^{39,53} A recent consensus statement published in 2010 highlights this fact: **“...no method to assess congestion prior to discharge has been validated.”**³⁹ While physical exam is currently the cornerstone of congestion assessment, it lacks sensitivity and inter-rater reliability.^{53,54} The ED is the beginning of AHF management for >75% of admitted patients;^{55,56} delays in diagnosis, misdiagnosis, and resultant delays in management are associated with greater morbidity and mortality.^{32,33}

Initial Therapy

[figure not shown]
IV loop diuretics are the mainstay of AHF management. Yet emergency physicians are often reluctant to use IV loop diuretics, largely influenced by small studies and retrospective studies suggesting an association with harm.

Nitrates are either recommended above diuretics or even to replace diuretics in popular blogs, podcasts, or online forums. Arguably, neither IV loop diuretics nor nitrates have definitive outcome data regarding efficacy or harm. This is evident in guidelines, where IV loop diuretics receive a class I, B indication, and nitrates a IIb, A recommendation. The evidence that does exist supports their use. Whether one should be used before another, both, how to combine them, and in whom, is not well defined.

Lung Ultrasound as an Endpoint

For years, the lungs have been considered ‘off-limits’ to ultrasound: with aerated lungs, the ultrasound beam is reflected and scattered due to acoustic mismatch.^{57,58} However, in the setting of pulmonary congestion, extra vascular lung water (EVLW) can be directly visualized and quantitated.⁵⁸⁻⁶⁰ Lung ultrasound measurement of B-lines are an objective, semi-quantitative measure of extra vascular lung water (EVLW).⁶⁰ B-lines are well-defined, vertical echogenic lines, originating from water-thickened interlobular septa.⁶⁰ (Figure 1) They are a marker of congestion.

LUS improves diagnostic accuracy and is highly reproducible.⁶¹⁻⁶⁷ Intra and inter-observer variability of B-line capture and summary have been reported as low as 5.1% and 7.4%, respectively.⁶⁸ In a recent meta-analysis, LUS was the best test to affirm the diagnosis of AHF, more than natriuretic peptide (NP) (likelihood ratio positive for the diagnosis of AHF by LUS was 7.4 (95% CI 4.2-12.8) and LR negative 0.16, (95% CI 0.05-0.51)).⁶¹ This may reflect the additional value of LUS when patients have chronically elevated NP levels. Recent guideline and consensus statements also support the use of LUS for diagnosis.⁶⁹⁻⁷³

Importantly, B-lines are a dynamic marker. In dialysis patients, B-lines decrease markedly pre/post dialysis.⁷⁴ In AHF patients, B lines generally decrease throughout hospitalization.^{75,76} However, persistence of B-lines pre-discharge identifies patients at higher risk for worse outcomes.^{76,77} B-lines even outperformed BNP as a prognostic marker.⁷⁵ Finally, serial measurement of B-lines are both easy to learn and perform.^{62,63,78-80} LUS is also low cost, and does not involve radiation. Computerized diagnostic aids have already been pilot tested with excellent results, demonstrating the ease of B-line scoring.⁸¹ Hand held machines perform as well as a standard ECHO platform or US machines.^{63,82} **The ease of LUS will facilitate its generalizability and dissemination.** Non-physicians may be future users of bedside LUS assessment, further supporting its generalizability.

2.3 POTENTIAL RISKS AND BENEFITS

[figure not shown]
2.3.1 KNOWN POTENTIAL RISKS

Overview. Current ED AHF treatment involves the use of non-invasive ventilation (NIV), IV loop diuretics, and IV, SL, or topical vasodilators. Each of these are highlighted in guidelines. However, the level of evidence supporting these treatments is relatively weak, with the strongest evidence supporting the use of IV loop diuretics. The evidence is even weaker for ED AHF treatment; for example, the AHA/ACC guidelines begin with hospitalization, highlighting the lack of evidence for ED AHF care. Although the evidence is weak, these medications are the current standard of care for AHF. There are NO novel therapies or unapproved treatments.

Common Risks. The greatest risks are not necessarily different than those already associated with these therapies. However, the risk may or may not be increased due to use of these treatments in a guided protocol strategy or when one therapy (nitrates or diuretics) are used initially over the other. To mitigate these risks, this study is being conducted in an ED setting, where ICU level care is routinely provided. If needed, rescue therapy with either drug (or additional therapies) may be provided.

For IV loop diuretics, commonly encountered risks include potential acute kidney injury (AKI) and over diuresis leading to hypovolemia which can lead to circulatory collapse and possibly vascular thrombosis and embolism, particularly in elderly patients. Electrolyte depletion may also occur especially in patients receiving higher doses and a restricted salt intake. Hypokalemia may develop, especially with brisk diuresis, inadequate oral electrolyte intake, when cirrhosis is present, or during concomitant use of corticosteroids, ACTH, licorice in large amounts, or prolonged use of laxatives. Digitalis therapy may exaggerate metabolic effects of hypokalemia, especially myocardial effects. Per routine standard of care at each of the sites, electrolytes are routinely checked during the initial 24-48 hours of treatment. These will be recorded. However, should no further electrolytes be measured after admission, there will be no pre-discharge lab draw. While AKI may occur, more recent data suggests that failure to decongest is associated with greater risk for adverse outcomes than transient AKI. To add a margin of safety, only patients with an eGFR ≥ 45 will be enrolled. Finally, we will assess eGFR prior to discharge (if measured as part of standard of care) to better understand whether our proposed strategy-of-care is associated with worsening renal function.

For nitrates, the greatest risk is hypotension. Marked sensitivity to the hypotensive effects of nitrates (manifested by nausea, vomiting, weakness, diaphoresis, pallor and collapse) may occur at therapeutic doses. Syncope due to nitrate vasodilation has been reported. Vertigo, weakness, palpitation and other manifestations of postural hypotension may

develop occasionally, particularly in erect, immobile patients. All patients will have IV access for fluids, if needed. Of note, the ESC guidelines allow for the potential use of IV nitrates in patients with a SBP > 110mmHg and only recommend avoiding them if the SBP is < 110 mmHg. Another common side effect is headache which may be severe and persistent may occur immediately after use. This will be treated with Tylenol or other non-narcotic analgesic medication. Nitroglycerin may produce a burning or tingling sensation when administered sublingually. Flushing, drug rash, and exfoliative dermatitis have also been reported in patients receiving nitrate therapy.

Potential Risks from Ultrasound: There are almost no risks to the use of ultrasound. Ultrasound is what is currently used to visualize the fetus in pregnant patients. The same type of ultrasound will be used for this study. There is NO radiation involved. The biggest complaint from use of ultrasound is the gel placed on the probe or body to improve visualization of the US waves is often cold.

2.3.2 KNOWN POTENTIAL BENEFITS

Patients enrolled in this study may receive a benefit such as feeling better faster. If the study shows that a nitrate or furosemide first strategy leads to faster resolution of congestion, future studies may explore early treatment in more detail. If either strategy is not safe with the current study design, future patients may be spared the cost of ineffective ED AHF management, and spared the potential for any possible side effects.

3 OBJECTIVES AND PURPOSE

Objectives:

1: To determine whether a nitrate intense strategy safely reduces congestion, defined by LUS B-lines, better than a diuretic intense strategy.

2. To demonstrate feasibility of recruitment and compliance with study protocol to inform future study design and enrollment projections, an external site will also test our study protocol.

Purpose:

This pilot trial is designed to provide the necessary and sufficient information for a larger, definitive trial.

Hypothesis 1a: Nitrate intense treated patients will have less congestion, defined by LUS B-lines, than diuretic intense patients at 6 hours after start of treatment.

Hypothesis 1b: Nitrate intense treated patients will have greater dyspnea relief than diuretic intense patients at 6 hours after start of treatment.

4 STUDY DESIGN AND ENDPOINTS

4.1 DESCRIPTION OF THE STUDY DESIGN

A two-site, prospective, randomized, pilot trial comparing a nitrate intense vs. diuretic intense strategy. All potential ED patients will receive an initial LUS scan. Performing LUS is within the standard of care and will be done at no cost to patients. It is not frequently used however, either for diagnosis, prognosis, or to guide clinical therapy. However, treating clinicians will be blinded to these results. If clinicians choose to perform their own LUS, those patients will not be excluded. Patients who provide written informed consent and meet all inclusion and no exclusion criteria will be randomized 1:1 to either study arm. For randomized patients, study protocol will continue until there is a decrease in B-

lines to ≤ 15 or 6 hours of care has been delivered. Subjects who are hospitalized prior to the completion of the 6 hour protocol may continue on the protocol until the six hour treatment window is concluded. All images will be stored and overread by an independent, expert ultrasonographer blinded to treatment arm.

Safety of patients are paramount. If a potential life threatening etiology is identified, the clinical team will be made aware immediately, irrespective of randomization arm. These occurrences will be recorded in the eCRF. While this will be a rare event, we will a priori establish that an additional patient will be accrued into the study and an additional modified intent to treat population for analysis will be performed, excluding these patients where a life-threatening etiology was identified (i.e. pericardial tamponade).

For patients who do NOT meet eligibility criteria, the results of their LUS will be provided to the clinical team as requested.

4.2.1 PRIMARY ENDPOINT

The total number of B-lines at the conclusion of ED AHF management

Main Secondary Endpoints:

Dyspnea will also be assessed using a 5-point and 7-point Likert scale.

B-lines ≤ 15 at the conclusion of ED AHF management

4.2.2 EXPLORATORY ENDPOINTS

The following table lists the exploratory endpoints

Table 3: Exploratory Endpoints	
Total DAOOH through 30 days post-discharge	Association of B-lines at discharge and 30 day outcomes
Time to reach B-lines ≤ 15	Association of baseline, discharge, and change of b-lines with 30 day outcomes
Change in physical exam findings	All Cause readmissions, All cause ED re-visits

5 STUDY ENROLLMENT AND WITHDRAWAL

5.1 PARTICIPANT INCLUSION CRITERIA

- 1) Age ≥ 21 years
- 2) Presents with shortness of breath at rest or with minimal exertion
- 3) Clinical diagnosis of AHF and presence of > 15 total bilateral B-lines distributed in at least 4 zones on initial LUS
- 4) Hx of chronic HF and any one of the following:
 - i. Chest radiograph consistent with AHF
 - ii. Jugular venous distension
 - iii. Pulmonary rales on auscultation

- iv. Lower extremity edema
- v. BNP > 500pg/mL

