Dyspnea will be assessed at the baseline and 6 hours later (or closest time point prior to ER discharge using two instruments. Dyspnea will also be assessed at any time between D2 and D/C. A 7-point Likert scale to determine change from baseline: 1) markedly worse, 2) moderately worse, 3) minimally worse, 4) no change, 5) minimally improved, 6) moderately improved, 7) markedly improved. However, patients may not recall accurately how they felt at baseline or be uncertain about when baseline was supposed to be. Also, patients with severe symptoms who don't respond and patients whose symptoms were initially mild and have little room to improve may end up with similar change scores. Accordingly, symptoms were also assessed using an absolute scale. Change in dyspnoea can be calculated by subtracting scores. A 5-point Likert scale was used to document patients' current status: 1) not short of breath at all, 2) mildly short of breath, 3) moderately short of breath, 4) severely short of breath, 5) very severely short of breath.

Patients were placed at 45 degrees for all questioning. If patients were recently up and walking, at least 2 minutes of equilibration is required.

Change scores between responses at baseline and 6 hours on the 5-point Likert scale items and the VAS were calculated by subtracting the baseline value from the 6-hour value. These change scores were categorized as improvement, worsening and no change. Fisher's exact tests were used to compare the 3 groups by either definition on changes in the 5-point Likert scale

2. The comparison of binary endpoints (B-lines ≤ 15) will be performed using Chi-square or Fishers exact test, as appropriate.

As 15 B-lines have been previously shown to be associated with worse outcomes, a difference of 15 B lines will be considered significant for this study.

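### On the 5-point dyspnea scale, patients with no resting breathlessness at T00 cannot be classed as improved, so the categorised change score dilutes the comparison for Hypothesis 1b

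*Combined protocol and SAP*

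**What the plan says.** Inclusion criterion 2 (section 5.1) is met by a patient who "Presents with shortness of breath at rest or with minimal exertion". Neither section 5.1 nor section 5.2 sets a minimum dyspnea score.

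The method is under the secondary endpoints in section 10.4.3: "Patients were placed at 45 degrees for all questioning. If patients were recently up and walking, at least 2 minutes of equilibration is required". The 5-point scale records current status and begins "1) not short of breath at all, 2) mildly short of breath", rising to 5 for the worst state. Change is the 6-hour score minus the baseline score. "These change scores were categorized as improvement, worsening and no change", and the named test is: "Fisher's exact tests were used to compare the 3 groups by either definition on changes in the 5-point Likert scale".

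Dyspnea is also recorded on a 7-point scale, on which the patient reports change from baseline directly. Section 10.4.3 lists weaknesses of that scale: recall of baseline, uncertainty about when baseline was, and that severe non-responders and "patients whose symptoms were initially mild and have little room to improve may end up with similar change scores". It adds the absolute 5-point scale in response.

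Section 10.3 makes the full analysis set (FAS) the main set for secondary endpoints. Hypothesis 1b (sections 3 and 10.2) predicts greater dyspnea relief at 6 hours in the nitrate arm. No section says which scale decides it.

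**The concern.** Entry can rest on exertional breathlessness, but the score is in effect taken at rest. A patient breathless only on exertion can therefore start at the best value of the 5-point scale. A patient whose breathlessness has settled before T00 could do the same, since sections 5.3 and 7.3.1 allow enrollment at any point in the ED stay and only prefer the first 3 hours after rooming.

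Such a patient can be classed only as unchanged or worse, whatever the treatment does. The plan recognises that mild patients have little room to improve and adds an absolute scale. Subtracting baseline and categorising the difference then brings the same limit back. The rule also puts a patient who stays free of breathlessness in the same category as one who stays very severely breathless.

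Dyspnea is a main secondary endpoint with its own hypothesis, in a pilot meant to inform a definitive trial. A diluted difference on the 5-point scale could hide a real effect or mislead the planning of that trial.

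**Working it through.** **The plan's own figure.** Section 10.5 states 82% power for B-lines with 35 per arm, effect size 0.7 and two-sided 0.05. A difference of 7 B-lines at effect size 0.7 implies SD = 7/0.7 = 10. The two-sample t-test (noncentral t) gives 82.3%, so the figure reproduces. It concerns B-lines and is not affected by this point. The documents give no power or response rate for dyspnea.

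**The floor.** The 5-point scale runs from 1 to 5 and change = 6-hour score − T00 score. With T00 = 1, change lies between 1−1 = 0 and 5−1 = +4. Improvement needs a negative change, so it cannot occur.

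**Dilution.** Let f be the share of each arm with T00 = 1, and r the improvement rate among patients who can improve.

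- Share improved in an arm = (1−f)·r + f·0 = (1−f)·r
- Between-arm difference = (1−f)·(r₁−r₂)

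**Power.** Taken from the documents: 35 per arm, two-sided 0.05, Fisher's exact test. Assumed:

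- r is 70% vs 40%, or 80% vs 50%.
- f is the same in both arms.
- The outcome is reduced to improved vs not improved, a simplification of the planned three-category comparison.

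Power is the sum over all i, j from 0 to 35 of Bin(i; 35, (1−f)r₁) × Bin(j; 35, (1−f)r₂), counting only tables with Fisher p < 0.05.

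| f | True 30-point difference becomes | Power, 70% vs 40% | Power, 80% vs 50% |
|---|---|---|---|
| 0 | 30 | 62% | 69% |
| 5% | 28.5 | 56% | 62% |
| 10% | 27 | 51% | 54% |
| 20% | 24 | 42% | 41% |
| 30% | 21 | 35% | 32% |

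For example, at f=20% the rates 80% and 50% become 0.8×80% = 64% and 0.8×50% = 40%.

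**Loss from the floor itself.** Restricting the same test to patients with T00 of 2 or more at f=10% leaves about 0.9×35 ≈ 32 per arm at undiluted rates. Power is then 62% and 64%, against 51% and 54% with everyone included. The loss therefore comes from counting patients who cannot improve, and fewer patients without them give more power.

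**The case against.** Several points on the other side stand.

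- A reader might infer that these patients are reported as treatment failures. The documents do not support that. The category is no change, kept separate from worsening, and no responder or failure rule for dyspnea exists.
- A reader might infer that Hypothesis 1b cannot detect relief in these patients at all. That is not so: nothing stops a patient with a 5-point score of 1 from reporting improvement on the 7-point scale. That scale does not remove the concern, though, because section 10.4.3 names no test for it, criticises it on recall and room to improve, and does not say that it decides the hypothesis.
- Limited room to improve is only one of several reasons given for adding the absolute scale. The authors saw the issue; what remains is the narrower matter of the 5-point floor after subtraction.
- The size of f is unknown. Patients come to an ED short of breath, with a clinical AHF diagnosis and more than 15 B-lines in at least 4 zones, so f may be small. At f=5% the loss is about 6 to 7 points of power.
- The floor does not depend on arm, so randomization balances it in expectation. The endpoint is secondary and unpowered, and under the assumed rates its power is only 62–69% with no floor at all.
- Restricting the main test to patients with T00 of 2 or more would be a poor remedy. It departs from the FAS rule in section 10.3 and drops patients at 1 who get worse. It also relies on a pre-randomization score: section 7.3.4 lists the Likert scales in the T00 column where treatment starts, not under screening, and the trial is unblinded.

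**Conclusion.** The point holds for the 5-point scale. Under the stated rule, a patient scoring 1 at T00 can only be unchanged or worse, nothing in the plan keeps such patients out or adjusts for their baseline, and the difference in the proportion improved shrinks by the factor (1−f). Under the assumed improvement rates and the two-category simplification, power falls from 62–69% to 56–62% at f=5% and to 41–42% at f=20%. The factor (1−f) is exact when f is equal in the two arms; the power figures are illustrations, because neither f nor the rates are in the documents.

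It would be going too far to call this bias. The expected effect is dilution toward no difference, although chance imbalance in f is possible with 35 per arm. The primary B-line analysis is untouched. The change is worth making because the plan can avoid the floor with data it already schedules.

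**What to change.** In section 10.4.3, replace the Fisher test on categorised 5-point change with an FAS analysis of the 6-hour 5-point score as an ordinal outcome, adjusted for the T00 score. The proportional odds model that section 10.4.4 already names for days alive and out of hospital will serve. A patient who stays at 1 is then recorded at the best outcome, given where that patient started, and every randomized patient in the FAS is kept.

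State in sections 7.3.4 and 10.4.3 that the T00 dyspnea score is recorded before randomization. Report the number scoring 1 at T00 by arm, which also supplies f for the definitive trial. Give the categorised-change result, and a sensitivity analysis limited to T00 of 2 or more, as supportive. The same edit is a good place to say which scale decides Hypothesis 1b. Criterion 2 need not change.

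The cost is SAP wording, one protocol line on the timing of a score already scheduled, and slightly more analysis work. The main analysis would rest on the proportional odds assumption, and the power it recovers has not been calculated here.
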